Table 11-1:	Anticipated serious adverse events for the RLS population	39
Table 11-2:	Laboratory measurements	43
Table 11-3:	Required investigations and follow up for PDILI.....	45
Table 11-4:	PDILI laboratory measurements	47
Table 11-5:	PDILI information to be collected	48

LIST OF ABBREVIATIONS

AE	adverse event
ADHD	attention deficit hyperactivity disorder
ALP	alkaline phosphatase
ALT	alanine aminotransferase
AST	aspartate aminotransferase
BMI	body mass index
BP	blood pressure
CDMS	clinical data management system
CGI	Clinical Global Impressions
CPM	Clinical Project Manager
CRO	contract research organization
C-SSRS	Columbia-Suicide Severity Rating Scale
DBP	diastolic blood pressure
eCRF	electronic Case Report form
ECG	electrocardiogram
EoM	End of Maintenance
FDA	Food and Drug Administration
GCP	Good Clinical Practice
ICD	impulse control disorder
ICH	International Council for Harmonisation of Technical Requirements for Pharmaceuticals for Human Use
IGF-1	insulin-like growth factor-1
IMP	investigational medicinal product
IRB	Institutional Review Board
IRLS	International Restless Legs Rating Scale
IRT	interactive response technology
ISF	Investigator Site File
LTFU	long-term follow-up
MAO	monoamine oxidase
MedDRA	Medical Dictionary for Regulatory Activities
mMIDI	Modified Minnesota Impulsive Disorder Interview

PD	pharmacodynamic
PDILI	potential drug-induced liver injury
PK	pharmacokinetic
PLATFORM	Science 37 Platform
PS	Patient Safety
PT	preferred term
RLS	Restless Legs Syndrome
RLS-QoL	Restless Legs Syndrome-Quality of Life
RLS-6	Restless Legs-6 Rating Scales
SAE	serious adverse event
SBP	systolic blood pressure
SD	standard deviation
SFU	Safety Follow-Up
SOC	system organ class
SOP	Standard Operating Procedure
SS	Safety Set
ULN	upper limit of normal

This document cannot be used to support any marketing authorization application and any extensions or variations thereof.

1 SUMMARY

This is a Phase 3, remote, open-label, long-term follow-up (LTFU) study of monotherapy administration of rotigotine transdermal patch in adolescent subjects with idiopathic Restless Legs Syndrome (RLS).

The total study duration per subject will be approximately 14 months after study entry or until the investigational product development is stopped by the Sponsor. The study will include a Titration Period of up to 3 weeks (at maximum), a Maintenance Period of up to 1 year, a Taper Period up to a maximum of 4 days (de-escalation of study medication), and a 30-day Safety Follow-Up (SFU) Period.

During the Titration Period, the investigator should determine whether the subject has reached his/her optimal dose (with a maximum dose of 3mg/24h) prior to completing the scheduled assessments for that visit. Subjects who have reached their optimal dose will maintain that dose and complete the Titration Period without titrating to the next higher dose.

Up to 138 subjects are planned to be treated during the study, assuming that all subjects had tolerated the first dose level of rotigotine in the previous study in adolescent subjects with idiopathic RLS (eg, SP1006) and choose to rollover into the present study (RL0007). A single remote site in the USA is planned to be included in the study. The remote study model to be used in this study integrates telemedicine technology into the clinical research process and supports management of research activities, including data collection.

The primary objective of this study is to assess the long-term safety and tolerability of rotigotine treatment in adolescents with idiopathic RLS. The secondary objective of this study is to assess the long-term efficacy of rotigotine treatment in adolescents with idiopathic RLS.

Primary safety variables include adverse events (AEs) and withdrawals due to AEs. Other safety variables include changes from Baseline in the following: 12-lead electrocardiograms (ECGs), vital signs, hormone status, laboratory tests (hematology, clinical chemistry, and urinalysis), menstrual function, modified Minnesota Impulsive Disorders Interview (mMIDI), body weight, height, and body mass index (BMI).

Efficacy variables include changes from Baseline in the following: International Restless Legs Rating Scale (IRLS) sum score, Clinical Global Impressions (CGI) Item 1 score; and RLS-6 Rating Scales. All statistical analyses of the efficacy variables will be considered exploratory.

Other variables include the Subject Quality of Life and plasma concentrations of rotigotine.

Baseline values from SP1006 will serve as Baseline in RL0007.

2 INTRODUCTION

Restless Legs Syndrome, also known as Willis-Ekbom disease, is a common pediatric neurologic condition affecting 2% to 4% of school-aged children and adolescents, with about 25% to 50% of pediatric cases having moderate-to-severe symptoms. Restless Legs Syndrome has a significant impact on sleep, mood, cognition, and function, particularly sleep disturbance. Impairment is often manifested in behavioral and educational domains (Pichietti et al, 2013). Genetic factors, dopamine dysfunction, and low-iron stores may play a role in the pathophysiology of RLS (Simakajornboon et al, 2009). Current evidence supports relative iron deficiency and renal failure as potential aggravating factors for pediatric RLS. Periodic limb

movements in sleep and a family history of RLS among first-degree relatives are supportive of pediatric RLS (Pichietti et al, 2013).

The pediatric RLS diagnostic criteria were published in 2003 based on the consensus at a National Institutes of Health workshop (2002) sponsored in part by the International RLS Study Group. These diagnostic criteria were updated in 2013 by the International RLS Study Group (Picchietti et al, 2013). Ruling out RLS mimics was integrated as an essential element for RLS diagnosis.

Dopaminergic agents are the first choice treatment for RLS in adults; however, to date, no treatment for RLS has been approved for children. Small published reports suggest that dopamine agonists are effective in the management of RLS in children (Simakajornboon et al, 2009; Cortese et al, 2009; Muhle et al, 2008; Mohri et al, 2008; Konofal et al, 2005; Guilleminault et al, 2003).

The investigational medicinal product (IMP) is a transdermal formulation of the dopamine agonist rotigotine. The patch is applied to the skin and provides constant plasma concentrations. It was first approved by the European regulatory authorities for use in patients with Parkinson's disease in March 2006, and by the US Food and Drug Administration (FDA) in May 2007. Rotigotine transdermal system was approved by the FDA as a treatment for adult patients with RLS in April 2012.

The tolerability of rotigotine transdermal system appears to be within the range of what is known and expected from other dopamine agonists, except for application site reactions, which appear to be mild to moderate in the majority of cases (Perez-Lloret et al, 2013).

UCB has completed a Phase 2 pharmacokinetic (PK)/pharmacodynamic (PD) study in adolescent subjects 13 to 17 years of age, which showed a PK profile similar to that in adult subjects. Although the study was open-label and the sample size was small, the efficacy of rotigotine transdermal system in adolescent subjects also appeared similar to efficacy in adults. Improvements were observed in most efficacy parameters, including the IRLS, CGI Items 1 through 3, and RLS-6, indicating improvements in RLS symptoms and sleep. The purpose of this study is to further investigate the safety, tolerability, and efficacy of rotigotine in adolescent subjects 13 to 17 years of age.

A remote study model will be used to conduct this study. This model integrates telemedicine technology into the clinical research process and supports management of research activities, including data collection. As part of this model, study visits are completed using the unique technology platform called Science 37 Platform (PLATFORM), which is the backbone of the studies conducted via this model. PLATFORM is the software interface that connects subjects/legal representatives to their investigators/study teams through a study-issued smartphone. This technology will be used in combination with visits from mobile study personnel to subjects'/legal representatives' homes.

3 STUDY OBJECTIVES

The primary objective of this study is to assess the long-term safety and tolerability of rotigotine treatment in adolescents with idiopathic RLS.

The secondary objective of this study is to assess the long-term efficacy of rotigotine treatment in adolescents with idiopathic RLS.

4 STUDY VARIABLES

Baseline values from SP1006 will serve as Baseline in RL0007. Baseline values for the other safety variables were collected at Visit 1 of SP1006.

4.1 Safety variables

4.1.1 Primary safety variables

- Occurrence of treatment-emergent adverse events (TEAEs)
- Treatment-emergent adverse events leading to permanent withdrawal of study medication

4.1.2 Other safety variables

- Changes from Baseline (Visit 1, SP1006) in 12-lead ECGs
- Changes from Baseline (Visit 1, SP1006) in vital signs (including assessment of orthostasis)
- Changes from Baseline (Visit 1, SP1006) in hormone status
- Changes from Baseline (Visit 1, SP1006) in laboratory data (hematology, clinical chemistry, and urinalysis)
- Changes from Baseline in menstrual function for all female subjects
- Changes in mMIDI
- Changes from Baseline (Visit 1, SP1006) in body weight, height, and BMI

4.2 Efficacy variables

4.2.1 Secondary efficacy variables

- Changes from Baseline in IRLS sum score at Visit 9
- Changes from Baseline in CGI Item 1 at Visit 9
- Changes from Baseline in RLS-6 at Visit 9

There are no primary efficacy variables.

4.2.2 Other efficacy variables

- Changes from Baseline in IRLS sum score at all visits except Visit 9
- Changes from Baseline in CGI Item 1 at all visits except Visit 9
- Changes from Baseline in RLS-6 at all visits except Visit 9

4.3 Other variables

- Plasma concentrations of rotigotine
- Subject Quality of Life Questionnaire

5 STUDY DESIGN

5.1 Study description

This is a Phase 3, remote, open-label, LTFU study of monotherapy administration of the rotigotine transdermal system. Subjects entering this study from the previous rotigotine study in adolescents (SP1006) must have tolerated the first dose level of rotigotine in that study without meeting the withdrawal criteria.

The study will be conducted using the remote study model, which uses telemedicine technology (ie, PLATFORM, see [Section 2](#) for an overview) for interactions between the investigator/study staff and study subjects/legal representatives. Mobile study personnel will visit subjects'/legal representatives' homes to complete certain study procedures (eg, neurological exams, physical exams, ECGs, lab collections, and vital signs). Subjects are allowed to be up-titrated and down-titrated at the discretion of the investigator during the Maintenance Period.

The study will begin with a Titration Period of 3 weeks with the aim of achieving the individually optimized dosage. During the Titration Period, investigators should determine at each visit whether the subject has reached his or her optimal dose prior to completing the scheduled assessments. Once subjects have reached their optimal dose, they will maintain that dose and complete the Titration Period without titrating to the next higher dose.

Titration will be followed by a Maintenance Period of up to 1 year. Dose adjustment of rotigotine is allowed at any time during the Maintenance Period, based on clinical judgment up to a maximum dose of 3mg/24h. At the End of Maintenance (EoM), subjects will enter a 4-day Taper Period followed by a 30-day SFU.

Visits will be scheduled every week during the Titration Period, every 3 months for the Maintenance Period, and at the end of the SFU.

5.1.1 Study duration per subject

The total study duration per subject will be approximately 14 months after study entry or until the investigational product development is stopped by the Sponsor. The study will include a Titration Period of up to 3 weeks (at maximum), a Maintenance Period of up to 1 year, a Taper Period up to a maximum of 4 days (de-escalation of study medication), and a 30-day SFU Period.

The end of the study is defined as the last visit of the last subject in the study.

5.1.2 Planned number of subjects and site

Up to 138 subjects are planned to be treated during the study, assuming that all subjects had tolerated the first dose level of rotigotine in the previous study in adolescent subjects with idiopathic RLS (eg, SP1006) and choose to rollover into the present study (RL0007). A remote clinical study model in the USA is planned to be utilized in the study.

5.1.3 Anticipated regions and countries

This study will be conducted in the USA.

5.2 Schedule of study assessments

The schedule of study assessments is provided in [Table 5-1](#).

Table 5-1: Schedule of study assessments

	SC (± 3 days)	Titration Period ^a					Maintenance Period Year 1 ^a				SFU ^b (30 ± 5 days)	Unscheduled Visit
		V2	V3	V4	V5	V6	V7	V8	V9 ^d			
Visit	V1 ^c	D1	D8	D15	D22	D90 (M3)	D180 (M6)	D270 (M9)	D360 (M12)			
Day/Month	D-4											
Informed consent	X											
Demographics		X										
Eligibility criteria		X										
Withdrawal criteria		X	X	X	X	X	X	X	X		X	
Reproductive potential and birth control	X				X	X	X	X	X			
Brief physical examination										X		X
Neurological examination										X		
Telemedicine neurological examination					X	X	X	X		X		X
C-SSRS		X	X	X	X	X	X	X	X	X		X ^e
Vital signs					X	X ^f	X	X ^f	X			X ^g
Body weight, height, and BMI					X		X		X			
12-lead ECG					X				X			X ^g
Safety labs					X		X		X			X ^g
Urine drug screen					X		X		X			
Urine pregnancy test (females) (hCG)					X	X ^f	X	X ^f	X	X		X
Hormone status					X				X			X
PK sampling (blood)					X				X			

Table 5-1: Schedule of study assessments

Visit	SC (± 3 days)	Titration Period ^a					Maintenance Period Year 1 ^a				SFU ^b (30 ± 5 days)	Unscheduled Visit
		V2	V3	V4	V5	V6	V7	V8	V9 ^d			
Day/Month	D-4	D1	D8	D15	D22	D90 (M3)	D180 (M6)	D270 (M9)	D360 (M12)			
IRLS						X	X	X	X	X		
CGI						X	X	X	X	X		
RLS-6 Rating Scales						X	X	X	X	X		
mMIDI						X	X	X	X	X		X
Menstrual function						X		X		X		
Subject Quality of Life Questionnaire						X	X	X	X	X		
Recording of medication and procedures	X	X	X	X	X	X	X	X	X	X		X ^g
AE assessment	X ^h	X	X	X	X	X	X	X	X	X		X
Contact IRT	X	X	X	X	X	X	X	X	X	X		X
Dispense study medication		X ⁱ			X ⁱ	X ⁱ	X ⁱ	X ⁱ				X ^g
Return unused study medication			X	X	X	X	X	X	X	X		X ^g

AE=adverse event; BMI=Body Mass Index; CGI=Clinical Global Impressions; C-SSRS=Columbia-Suicide Severity Rating Scale; D=Day; ECG=electrocardiogram; EoM=End of Maintenance; EoT=End of Taper; hCG=human chorionic gonadotropin; IMP=investigational medicinal product; IRLS=International Restless Legs Rating Scale; IRT=interactive response technology; lab=laboratory; M=Month; mMIDI=modified Minnesota Impulsive Disorder Interview; PK=pharmacokinetic; RLS=Restless Legs Syndrome; SC=Screening; SFU=Safety Follow-Up; SoM=Start of Maintenance; V=Visit; WD=withdrawal

Note: It is preferred that a subject directly continue from SP1006 into RL0007; however, if a subject cannot directly continue into RL0007, the subject has until the SFU Visit of SP1006 to enroll in RL0007.

Note: Visit 1 should occur 4 days prior to Visit 2/Day 1 to allow for direct-to-subject shipment of study medication. Visit 2/Day 1 is the first day of study medication exposure. All subsequent visits are calculated based on Visit 2/Day 1.

Note: Visit 5 is the end of the Titration Period and start of the Maintenance Period. Visit 9 is the end of the Maintenance Period and the start of the Taper Period.

Table 5-1: Schedule of study assessments

Visit	SC (± 3 days)	Titration Period ^a					Maintenance Period Year 1 ^a				SFU ^b (30 ± 5 days)	Unscheduled Visit
		V2	V3	V4	V5	V6	V7	V8	V9 ^d			
Day/Month	D-4	D1	D8	D15	D22	D90 (M3)	D180 (M6)	D270 (M9)	D360 (M12)			

Note: The visit window for Screening is ± 3 days relative to Day -4. The visit window for Titration Visits is ± 3 days relative to Visit 2/Day 1 (day of first dose).

The visit window for visits during the Maintenance Period, including the End of Maintenance Visit, is ± 14 days relative to Visit 5. The Taper Period, which will last up to a maximum of 4 days, will start after the End of Maintenance Visit (Visit 9). Note that there are no planned visits during the Taper Period. The visit window for Safety Follow-Up Period is 30 days ± 5 days relative to the end of the Taper Period.

^a Subjects who are down-titrated during the Titration Period will automatically enter the Maintenance Period. Subjects are allowed to be up-titrated and down-titrated at the discretion of the investigator during the Maintenance Period.

^b All subjects are required to complete the SFU Visit 30 days ± 5 days after the final patch removal (end of the Taper Period).

^c Assessments for Visit 1 of RL0007 should be performed on the same day as the evaluation in the previous rotigotine study (Visit 9 of SP1006).

^d Taper Period de-escalation study medication will be part of the IMP that will be shipped with Visit 8.

^e Required if an AE is the reason for the Unscheduled Visit.

^f May be performed at the subject's/legal representative's home, excluding temperature and respiration rate, by the subject/legal representative if mobile study personnel are not able to be physically present at the home.

^g Assessments to be performed are at the investigator's discretion.

^h From Visit 10 of SP1006, if available. If not available from Visit 10 of SP1006, should be collected within 2 weeks of that visit in SP1006.

ⁱ Study medication to be shipped to subject's home to be available no later than this date.

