6 SELECTION AND WITHDRAWAL OF SUBJECTS

6.1 Inclusion criteria

To be eligible to participate in this study, all of the following criteria must be met:

1. An Institutional Review Board (IRB)-approved written Informed Consent form is signed and dated by the subject or by the parent(s) or legal representative. The Informed Consent form or a specific Assent form, where required, will be signed and dated by minors.
2. Subject/legal representative is considered reliable and capable of adhering to the protocol (eg, able to understand and complete all questionnaires and diaries), visit schedule, or medication intake according to the judgment of the investigator.
3. Subject weighs $\geq 40\text{kg}$.
4. Subject has completed at least one dose step in SP1006, a previous study of rotigotine in adolescents with RLS, without meeting withdrawal criteria.
5. Female subjects must be surgically incapable of childbearing, or effectively practicing an acceptable method of contraception (oral/parenteral/implantable hormonal contraceptives, intrauterine device, or barrier and spermicide). Abstinence is an acceptable method. Subjects must agree to use adequate contraception during the study and for 4 weeks after their final dose of study drug.
6. Subject is expected to benefit from participation, in the opinion of the investigator.

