7.2 Treatments to be administered

7.2.1 Titration Period

The study will begin with a Titration Period of up to 3 weeks (at maximum) with the aim of achieving the individually optimized dosage (with a maximum dose of 3mg/24h).

Subjects will be treated at Visit 1 using the following dose titration schedule until their optimal dose is reached ([Table 7-2](#)).

Table 7-2: Dose titration schedule until optimal dose is reached

Visit/Day	Dose
Visit 2/Day 1	1mg/24h
Visit 3/Day 8	2mg/24h
Visit 4/Day 15	3mg/24h

During the Titration Period, the investigator should determine whether the subject has reached his/her optimal dose prior to completing the scheduled assessments for that visit. Subjects who have reached their optimal dose should continue at that dose and remain in the Titration Period until they have reached Visit 5 and enter the Maintenance Period. Subjects are allowed to be up-titrated and down-titrated at the discretion of the investigator during the Maintenance Period.

The optimal dose for each subject will be defined as absence of or maximal reduction in RLS symptoms without intolerable side effects. If the investigator judges that the subject is likely to benefit from a dose increase, then dose titration should continue. If the investigator judges that the subject is unlikely to benefit from a dose increase, then the dose is defined as optimal.

If AEs occur during the Titration Period that are thought to be the result of excessive dopaminergic stimulation (eg, intolerable nausea/vomiting), subjects should be down-titrated to their previous dose level and continue at that dose until they reach Visit 5 and enter the Maintenance Period.

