8 STUDY PROCEDURES BY VISIT

8.1 Visit 1 (Screening/Day -4)

Prior to any study activities, subjects will be asked to read and sign an Informed Consent form and/or Assent form that has been approved by an IRB and which complies with regulatory requirements. Subjects will be given adequate time to consider any information concerning the study, given to them by the investigator or designee. As part of the Informed Consent procedure, subjects and parent/legal representative will be given the opportunity to ask the investigator any questions regarding potential risks and benefits of participation in the study.

Assessments for Visit 1 of RL0007 should be performed on the same day as the final evaluation visit of the previous rotigotine study (Visit 9 of SP1006).

The following assessments will be performed:

- Obtain informed consent. See [Section 14.1](#) for a description of the informed consent process for the remote study model.

Information and procedures listed below will be collected/completed by the investigator and/or study staff, as appropriate, via a telephone or telemedicine call with the subject/legal representative:

- Reproductive potential and birth control

Additional assessments and procedures are listed below.

- Recording of medication and procedures. Medications and procedures will be reviewed with the subject/legal representative by the investigator/designated study staff via a telephone or telemedicine call and noted as part of the subject's study record.
- AE assessment. All AEs will be assessed and reviewed throughout the study.
- Contact IRT. Once eligibility is confirmed (see above), the IRT will be contacted to obtain the study medication kit numbers for the Titration Period.

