8.2.1 Visit 2 (Day 1)

Subjects will be contacted via telemedicine call. The following assessments will be performed:

- Demographics
- Eligibility criteria
- Withdrawal criteria
- C-SSRS (Since Last Visit version)

Additional assessments and procedures are listed below.

- Recording of medication and procedures: See [Section 8.1](#).
- AE assessment: See [Section 8.1](#).
- Contact IRT: The IRT will be contacted.
- Dispense study medication. Study medication for the Titration Period will be shipped to the subject's/legal representative's home/preferred address to be available for the first dose of study medication in RL0007 at Visit 2/Day 1. See [Section 7.5](#) for the description of the direct-to-subject shipment process for the remote study model.

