8.2.3 Visit 5 (Day 22)

The Titration Period ends at Visit 5.

Information and procedures listed below will be collected/completed by the investigator and/or study staff, as appropriate, via a telephone/telemedicine call with the subject/legal representative.

- Withdrawal criteria
- Reproductive potential and birth control
- Menstrual function for all female subjects
- Telemedicine neurological examination

The assessments listed below will be completed by the subject/subject's legal representative's local health provider or mobile study personnel will be sent to the subject's/legal representative's home. Records of the procedures will be obtained, with information noted as part of the subject's study record.

- 12-lead ECG

For lab collections and procedures listed below, mobile study personnel will be sent to the subject's/legal representative's home for sample collections. Samples will be prepared and sent to a central laboratory for processing and analysis, and results will be provided to the study site.

- Vital signs
- Body weight, height, and BMI
- Safety laboratory tests
- Urine drug screen
- Urine pregnancy test for all female subjects
- Hormone status
- PK sampling—record sampling time, time of application of study medication, and application site of study medication in eCRF

Assessments listed below will be completed either by the subject or investigator/trained study staff, as required. Assessments that require interviews will be completed via a telephone or telemedicine call.

- C-SSRS (Since Last Visit version)
- IRLS
- CGI
- RLS-6
- mMIDI
- Subject Quality of Life Questionnaire

Additional assessments and procedures are listed below.

- Recording of medication and procedures: See [Section 8.1](#).
- AE assessment: See [Section 8.1](#).
- Contact IRT: The IRT will be contacted to obtain study medication kit numbers for the Maintenance Period.
- Dispense study medication. Study medication for Visit 5 will be shipped to the subject's/legal representative's home/preferred address to be available for that visit. See [Section 7.5](#) for the description of the direct-to-subject shipment process for the remote study model.
- Return unused study medication. See Section [8.2.2](#).

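### RL0007 requires no urine pregnancy test before the first patch and cites no SP1006 result in its place

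*Protocol*

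**What the plan says.** In Protocol Section 5.2, the Table 5-1 row "Urine pregnancy test (females) (hCG" is marked at Visits 5 to 9, the Safety Follow-Up (SFU) Visit and Unscheduled Visits. Visits 1 to 4 carry no mark. The table notes make Visit 2/Day 1 the first day of exposure.

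The visit lists match the table:

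- Visit 1 (Section 8.1) covers consent, the remote item "Reproductive potential and birth control", medication and adverse-event recording, and kit allocation: "Once eligibility is confirmed (see above), the IRT will be contacted to obtain the study medication kit numbers for the Titration Period".
- Visit 2 (Section 8.2.1) is the day of first dosing and is remote: "Subjects will be contacted via telemedicine call". Eligibility and withdrawal criteria are reviewed; no pregnancy test is listed.
- Visits 3 and 4 (Section 8.2.2) list none.
- Visit 5 (Section 8.2.3) is the first to list "Urine pregnancy test for all female subjects".

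Inclusion criterion 5 states: "Female subjects must be surgically incapable of childbearing, or effectively practicing an acceptable method of contraception". Abstinence also counts. No criterion asks for a negative test or excludes pregnancy. Withdrawal criterion 10 and Section 11.2 take a subject off study once a test is positive.

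Visit 1 is meant to fall on the day of SP1006 Visit 9. However, "if a subject cannot directly continue into RL0007, the subject has until the SFU Visit of SP1006 to enroll in RL0007".

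**The concern.** The protocol treats pregnancy as incompatible with continued treatment and tests at every scheduled visit from Visit 5 through SFU. It omits the check at the one point where exposure could be prevented rather than stopped. Eligibility is confirmed before drug is shipped and reviewed again on the day of the first patch, and neither step includes a test. A contraception rule and a birth-control question lower the probability of pregnancy but do not detect one.

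A rollover study can reasonably rely on a recent result from its parent study. Here the protocol does not say that it does, which result it would use, or how old that result may be. At stake is avoidable fetal exposure in adolescents. No efficacy or safety estimate is biased by this.

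**Working it through.** The plan gives no figure of its own here, so the check is a comparison of texts plus day arithmetic.

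**Inputs.** First patch: Day 1 (Table 5-1 notes). Visit 5: Day 22, ±3 days (Table 5-1; Section 8.2). Visit 1: Day -4, ±3 days (Table 5-1 notes). Titration steps: 1, 2 and 3 mg/24h from Days 1, 8 and 15 (Table 7-2). Subjects at their optimal dose "remain in the Titration Period until they have reached Visit 5" (Section 7.2.1).

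**1. First patch to first required test, under Sections 7.2.1 and 8.2.**
- Nominal: 22 − 1 = 21 days.
- Window: Day 19 to Day 25, so 19 − 1 = 18 to 25 − 1 = 24 days.
- Daily patches before the test: 21 (18 to 24). On nominal days, a subject titrated to the top has 7 days each at 1, 2 and 3 mg/24h.

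**2. The same interval if a subject enters Maintenance early.** Table 5-1 footnote a moves down-titrated subjects straight to Maintenance, and SAP Section 3.2.3 allows Visit 5 once the optimal dose is reached. Both conflict with Section 7.2.1. For illustration, Visit 5 procedures on Day 15 would put the test at 15 − 1 = 14 days, and on Day 8 at 8 − 1 = 7 days. The interval shortens, but the test still follows the first patch.

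**3. Age of an SP1006 result, if one exists.**
- Direct rollover: SP1006 Visit 9 coincides with RL0007 Visit 1, so a result from that day would be 4 days old at first patch (4 − 3 = 1 to 4 + 3 = 7).
- Delayed entry: the timing of the SP1006 SFU Visit is not given. *Assumption:* it mirrors RL0007, with a taper of 0 to 4 days and then 30 ± 5 days. The SFU Visit then falls 0 + 25 = 25 to 4 + 35 = 39 days after SP1006 Visit 9. For the latest entrant, the first patch could come up to 39 + 7 = 46 days after Visit 9 and the first RL0007 test up to 46 + 24 = 70 days after it.

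**4. Spacing of later tests.** By Table 5-1 days, 90 − 22 = 68 and then 90 each time (90 throughout if counted from the start of Maintenance, as in SAP Section 3.2.3). A result a few days old would therefore sit well within the protocol's own practice. The defect is that no result is required at all.

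**5. Other text that might supply the check.**
- The Visit 1 reproductive item is a telephone or telemedicine question.
- Withdrawal criterion 10 is reviewed at Visits 2 to 4 but needs a positive test, and none is scheduled by then.
- Tests at Unscheduled Visits are discretionary (Section 8.7).
- The urinalysis baseline is SP1006 Visit 1 (Section 4.1.2). That is a reference for change taken at the start of the earlier study, not an RL0007 entry check.

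None of these requires a negative result before dosing.

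**The case against.** The strongest reply is that the harm depends on a schedule nobody can see here. If SP1006 tested at both Visit 9 and its SFU Visit, direct rollovers and the latest entrants would have a recent result, and the gap would be little more than a missing cross-reference. RL0007 also looks like a deliberately lean rollover. It requires a weight of at least 40 kg (inclusion criterion 3) yet first measures weight at Visit 5, so it evidently leans on SP1006 data without always naming the source. Where it does name one, only the C-SSRS in exclusion criterion 2a is a true entry check; the QTc and safety baselines are change references. Silence about a pregnancy result therefore does not show that none existed. In addition, contraception is mandatory, every subject has already used rotigotine, staff can be reached at any time, and the study was terminated early (SAP Section 1).

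Much of this stands as a limit on size. It rules out two inferences that a reader might draw:

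- *Female subjects went untested into dosing.* The documents describe what RL0007 requires, not what was done.
- *The gap matters mainly for delayed entrants.* They lose the same-day link to SP1006 Visit 9, but they may have been tested at the SP1006 SFU Visit. If Visit 9 had no test, direct rollovers are exposed too. The documents do not rank the two groups.

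The objection does not supply a requirement. An unstated result from another study is not a condition of dosing in this one, and the other controls are not tests. Early termination limits the use of a change in this trial but does not make the schedule sound.

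**Conclusion.** The point holds as a gap in subject protection. RL0007 requires no pregnancy test before the first patch and cites no SP1006 result instead. The first listed test is nominally 21 days after dosing starts (18 to 24 with the window). A reader might take three weeks as fixed for everyone; footnote a and SAP Section 3.2.3 leave room for an earlier Visit 5 in some subjects, though not for a test before Day 1.

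How many subjects lack a recent result is unknown and could be zero. The only bound given is the planned maximum of 138 subjects of both sexes. The absence of a test rests on Table 5-1 and the visit lists, which agree. The 39-, 46- and 70-day figures for delayed entry rest on the assumption that SP1006 follow-up mirrors RL0007. This is a cheap improvement worth making, not a threat to any estimate.

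**What to change.** In Table 5-1 and Sections 8.1 and 8.2.1, require a documented negative urine pregnancy test for female subjects before the first patch.

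- Accept a dated SP1006 result within a short stated window. Seven days before the first patch is a workable example, because it equals the longest allowed interval from Visit 1 to Visit 2. The documents give no basis for accepting only a result from the day of Visit 1.
- Otherwise send a home kit with the titration shipment. Shipment can still follow the Visit 1 eligibility check, but no patch is applied until a negative result is confirmed on the Visit 2 call. A positive result means no dosing and return of the shipment.

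The cost is one kit per female subject without an accepted result, one extra check on an existing call, an occasional returned shipment, and sometimes a short delay to Day 1. Home urine testing is already used at Visits 6, 8 and SFU (Sections 8.3.1, 8.3.3 and 8.5), and return materials are already supplied (Section 7.6). As this study has stopped, the practical steps are to check whether female entrants had a documented result before dosing and to carry the rule into later rollover protocols.
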